DURATION	8 weeks for the total study (each volunteer will test the different products only once, each participant will be required to be present at the laboratory for 2 days only)

REFERENCE DIAGRAM

1. INTRODUCTION

1.1 WHY HANDWASHING

Diarrhoeal diseases are a common cause of morbidity and the leading cause of death among children under five, accounting for 19% of mortality in this age group [1]. Most of all diarrhoeal deaths of children under five years are in Africa and South East Asia [2]. The vast majority of diarrhoeal diseases are caused by bacteria, viruses and protozoa, mainly found in human faeces which are spread from the stool of one person to the mouth of another. Hands can act as a vector for transmission of faecal pathogens, either via direct person-to-person transmission or by contaminating food that is later consumed [3]. Hand washing with soap after defecation and before handling food is the most effective mechanism for interrupting diarrhoeal disease transmission, with the potential to reduce it by 23% to 48% [4-6]. Hands are also transmission vectors for respiratory infections, and handwashing with soap can also reduce respiratory illnesses by an average 21%, [7].

Handwashing rates are sub-optimal globally [8], but this is of particular concern in humanitarian emergencies when faecal-oral disease risk increases [9-10], and is often a leading cause of morbidity and mortality. Access to hand washing facilities, water and soap in humanitarian emergencies is limited. Those affected by emergencies typically rely on non-government organisations (NGOs) to distribute soap and water. However this approach alone has not been found to increase handwashing rates. Partly this is because when water and soap are scarce they are prioritised for tasks other than handwashing. Secondly it is often difficult for NGOs to meet the demand of beneficiaries – particularly in protracted crises. The Sphere Standards [11] recommend that in an emergency one person should have one 250g bathing soap per month and at least 6 litres of water per day. But in 2016, there were 65.6 million people displaced [12] from their homes due to conflict, persecution and crises and therefore meeting the needs of all these people is a mammoth logistical task. In many camp settings toilets and associated handwashing facilities (if present) are shared. Invariably the soap that NGOs provide is rarely placed at the handwashing facility as people worry about it being stolen and used by others. As such individuals are required to walk to the toilet carrying their own bar of soap. When they use the shared (and often unclean) toilet there is nowhere to store the soap hygienically. Then after washing their hands with the soap the individual has to walk back to their shelter with the slimy bar of soap, meaning that their hands are still covered with soap at the end of the process. Of course in practice this is far too inconvenient and so hands are normally just rinsed with water, if at all.

1.2 THE SUPERTOWEL

The Supertowel has been designed as a soap alternative for these types of emergency situations. The Supertowel is a durable fabric with a permanent anti-microbial bonding. The treated fabric must be dipped in water and then rubbed against the hands so that pathogens will be transferred to the fabric where they will be killed. Several laboratory test have demonstrated the bactericidal effect of the fabric against different bacteria (Appendix 1). The anti-microbial technology is achieved by long chains of carbon atoms attached to positively charged nitrogen atoms bonded to a silica layer of the fabric. The positively charged layer attracts negatively charged microbes including bacteria and fungi causing membrane disruption of the microbes. The Supertowel will kill microbes efficiently and within seconds once the microbe is on the towel. As the bonding is permanent the fabric does not call for replacement until it is damaged or lost. The Supertowel provides an alternative to large-scale soap distribution. It could be beneficial to emergency responders as it will be easier (smaller and lighter) to distribute and last longer than soap, negating the need for frequent distributions. The Supertowel will reduce water wastage associated with hand washing and reduce drainage problems that are often seen around hand washing facilities. The Supertowel will also be beneficial to those effected by emergencies as it can easily be carried by users all the time, making hand cleaning more convenient.

1.3. RESEARCH TO DATE

Over the last two years our consortium has been able to prove, under controlled laboratory conditions, that hand cleaning with the Supertowel is more efficacious than handwashing soap and water [13]. Our subsequent field study in a refugee camp in Northern Ethiopia indicated that the Supertowel is an acceptable and desirable product among crisis-affected populations and is likely to result in more frequent handwashing in these difficult circumstances [14].

The aim of this study is to develop greater evidence on whether the Supertowel remains as efficacious when used under conditions which mimic “real-world hand cleaning conditions”. This will be tested through a set of controlled laboratory experiments with healthy volunteers in India.

1.4 RATIONALE FOR CURRENT STUDY

To test the efficacy of the Supertowel as a hand-cleaning product under different “real-world” conditions.

2. STUDY OBJECTIVES

Test the efficacy of the Supertowel as a hand-cleaning product using simulations of ‘real-world’ hand cleaning conditions. This will be achieved by using an in vivo design with healthy volunteers in India and a protocol adapted from the European Committee for Standardization protocol (EN 1499) [15].

Tests will be designed to explore the following objectives:

- Is the Supertowel as efficacious as soap if used for hand-cleaning for a short period of time (ie. 15 seconds)?
- Is the Supertowel as efficacious as soap if used for hand-cleaning when moist rather than soaking wet?
- Is the Supertowel efficacious for hand-cleaning if soiled and oily?
- Is a Supertowel soaked in contaminated water and then used for hand cleaning more efficacious than handwashing with soap and contaminated water?

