The Supertowel will be soaked in water by submersing it completely in a bucket filled with tap water. The water on the Supertowel will then be squeezed out so that it is not dripping. The Supertowel will be weighed before soaking and after squeezing. Volunteers will clean their pre-contaminated hands with the damp Supertowel for 60 seconds.

- Control: Handwashing with bar soap and water for 60 seconds

The control group will wash their pre-contaminated hands with normal bar soap and water for 60 seconds by following the “WHO guidelines for handwashing when hands are visibly soiled” (a diagram of the steps was given to them, appendix). After handwashing, hands will be allowed to dry for 3 minutes.

Procedure 3.

- Treatment: Hand cleaning for 60 seconds with a Supertowel that has been soaked in contaminated water.

A Supertowel will be soaked in water which has artificially contaminated with non-pathogenic E.coli. The water will be designed to mimic highly contaminated grey water so it will be contaminated at 2,000 cfu/100 ml which is double the acceptable level of contamination for handwashing. Volunteers will clean their pre-contaminated hands with the contaminated Supertowel for 60 seconds.

Control: Handwashing with bar soap and water for 60 seconds.

Water which is contaminated with non-pathogenic E.coli. at 2,000 cfu/100ml will be stored in a bucket which has a tap at the base. The control group volunteers will wash their hands with the contaminated water and bar soap for 60 seconds. They will follow the “WHO guidelines for handwashing when hands are visibly soiled” (a diagram of the steps will be given to them). After handwashing, hands will be allowed to dry for 3 minutes.

Procedure 4.

- Treatment: Hand cleaning for 60 seconds with a Supertowel that is visibly dirty and oily.

The Supertowel will be made visibly dirty and oily for example, by immersing it in a mix of 5 grams of sterile soil (previously autoclaved), 5 ml of clean cooking oil and 100 ml of water (we will play in advance, to find out the most appropriate amounts of these products). The Supertowel will be rubbed against itself to ensure the soil and oil are spread out across the surface of the Supertowel. Volunteers will clean their pre-contaminated hands with the dirty Supertowel for 60 seconds.

- Control: Hand cleaning for 60 seconds with a clean Supertowel.

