9. STATISTICS AND DATA ANALYSIS

For all the procedures, log counts from the left and right hands of each subject will be averaged separately, for both pre and post values. The arithmetic means of all individual \log_{10} reduction values will be calculated. Statistical analysis will be performed with the Statistical Package STATA version 13.0. Wilcoxon matched-pair signed ranks test will be used to test for differences between each *Supertowel procedure* and their reference condition. The new procedure (*Supertowel under different conditions*) will be considered as effective as the reference product (soap) if the mean \log_{10} reduction factor is not significantly smaller for the former than for the latter. Because of the confirmative nature of the test on this application, the level of significance is set at $p = 0.1$. The test is to be used one-sided. The

discrimination efficiency of the test procedure described has been set to detect a difference between the two mean log reduction factors of approximately 0.6 log at a power of 95%. Data and all appropriate documentation will be stored for a minimum of 5 years after the completion of the study.

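### Objective 4 asks whether the Supertowel is better than soap with contaminated water, but the only verdict Section 9 defines against soap is equal effectiveness

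*Combined protocol and SAP*

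**What the plan says.** Section 2 lists four objectives. The first two ask about parity with soap; the second, for example, reads "Is the Supertowel as efficacious as soap if used for hand-cleaning when moist rather than soaking wet". The fourth asks for more: "Is a Supertowel soaked in contaminated water and then used for hand cleaning more efficacious than handwashing with soap and contaminated water".

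Section 6.2.2 carries objective 4 into Procedure 3. The treatment arm is "Hand cleaning for 60 seconds with a Supertowel that has been soaked in contaminated water", and the control is a 60-second wash with bar soap and water contaminated to the same level. The procedure has no decision rule of its own.

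Section 9 holds the only analysis rules:

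- The test: "Wilcoxon matched-pair signed ranks test will be used to test for differences between each" Supertowel procedure and its reference.
- The verdict: the new procedure "will be considered as effective as the reference product (soap) if the mean" log reduction meets a criterion.
- The criterion: the "reduction factor is not significantly smaller for the former than for the latter".
- The level: "Because of the confirmative nature of the test on this application, the level of significance is set at" 0.1.
- The sidedness: "The test is to be used one-sided".

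Section 9 also states 95% power for a difference of about 0.6 log. It gives no SD and, in that sentence, no sample size. Sections 3 and 6.3 put Procedure 3 in round 1, with 16 volunteers who each use every method.

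**The concern.** The one direction Section 9 spells out is *smaller*, and the one verdict it defines against soap is parity. Objective 4 needs the opposite direction and a different verdict. An analyst who applies the written rule to Procedure 3 can conclude only that the Supertowel is, or is not, as effective as soap. A tie and a real advantage then get the same verdict.

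Two things could go wrong. The parity verdict could be reported as if it answered objective 4, although it is designed to be easy to reach when there is no difference. Or the one-sided test could be turned upward after the results are known, with no record that this was intended. The plan calls the test confirmatory, so the direction should be fixed in advance.

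Only Procedure 3's conclusion is affected. Data collection and the other comparisons are not.

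**Working it through.** **Inputs.** n = 16 pairs (Sections 3 and 6.3); one-sided level 0.1, and a 0.6 log difference with 95% power (Section 9). Assumed: no ties or zero differences; normally distributed paired differences wherever power is quoted.

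**1. The plan's power statement.** It cannot be reproduced directly because no SD is given. Assuming that it refers to 16 pairs, solve for the SD of the paired differences:

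- Normal approximation: SD = 0.6 × √16 / (1.282 + 1.645) = 2.4 / 2.926 = 0.82.
- Noncentral t: 0.80.
- Signed-rank test, by simulation: about 0.77.

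The figures below use 0.77, with 0.6 to 1.0 as the range. The 95% at 0.6 log is therefore true by construction.

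**2. Exact size of the test (needs no SD).** The signed-rank statistic for n = 16 has 2^16 = 65,536 equally likely sign patterns under equality.

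- Tail statistic ≤ 42: 6,318 patterns; 6,318 / 65,536 = 0.0964.
- Tail statistic ≤ 43: 6,928 patterns; 0.1057, above 0.1.

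The test therefore rejects at 42 or below, with an attained one-sided level of 9.6%.

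**3. The written rule under equality.** P(not significantly smaller) = 1 − 0.0964 = 0.9036, or 90.4%. Read as evidence of superiority, the rule would be wrong 90.4% of the time when the methods are equal.

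**4. Written rule against an upward test.** Simulated, 400,000 samples of 16 pairs per cell, SD 0.77 (range for SD 0.6 to 1.0 in brackets):

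| True Supertowel gain | Written rule met | Upward test rejects at 0.1 |
|---|---|---|
| 0 (exact) | 90.4% | 9.6% |
| 0.3 log | 99.7% (99.9% to 99.2%) | 57% (72% to 44%) |
| 0.6 log | over 99.9% (over 99.9% throughout) | 95% (99% to 83%) |

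The written verdict barely moves between a tie and a 0.6 log advantage. The upward test separates them.

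**5. Using both rules on the same pairs.** The positive and negative rank sums add to 16 × 17 / 2 = 136, so both cannot be 42 or less and the two rejections exclude each other. Under equality:

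- significantly larger: 9.6%
- significantly smaller: 9.6%
- neither: 1 − 2 × 0.0964 = 80.7%
- either: 2 × 0.0964 = 19.3%

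The false superiority rate is 9.6% whether or not the downward rule is kept.

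**6. What the downward rule contributes.** If the Supertowel is truly 0.6 log worse, the written rule withholds the parity verdict about 95% of the time at SD 0.77 (99% to 83% for SD 0.6 to 1.0). An upward test alone would report only that superiority was not shown, as it does about 90% of the time at equality.

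**The case against.** The strongest reply is that the plan already contains nearly everything objective 4 needs. Section 9 plans a test for differences between each Supertowel procedure and its reference, one-sided at 0.1; Section 6.2.2 fixes the comparator; and the objective's wording gives the direction. The parity sentence defines one verdict and does not forbid reporting a significantly larger reduction. Section 2 also describes the tests as exploring the objectives.

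Much of this stands. A reader might infer that objective 4 has no planned analysis or no route to an answer. The documents do not support that, because test, comparator, level and sidedness are all there. What does not stand is that nothing is missing. The only direction written beside the one-sided test is the opposite of the one objective 4 needs, and no sentence assigns a conclusion to a significantly larger reduction. The exploratory wording helps little, because Section 9 justifies its level by the test's confirmatory nature.

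Two further inferences are tempting:

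- That the upward test should replace the existing rule for Procedure 3. It should not. Replacement would give up the ability to report that the Supertowel did worse, and the 19.3% in step 5 is no argument for it, since that figure adds two opposite errors and leaves the false superiority rate at 9.6%.
- That the aim in Section 1.3 shows parity with soap was meant all along. That section first says the Supertowel outperformed soap, then asks whether it stays as efficacious under realistic conditions. This may mean keeping its own performance, so it settles nothing.

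**Conclusion.** The point holds as a mismatch between one objective and the decision rule, and it should be fixed. Applied as written to Procedure 3, Section 9 answers a parity question where objective 4 asks a superiority question, and meeting the written rule is not evidence of superiority. No figure in the plan is shown to be wrong.

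The 90.4%, 9.6% and 19.3% rest only on n = 16, the 0.1 level and the absence of ties and zero differences. The power figures are illustrative. They depend on normal differences and on an SD of 0.77, which is back-solved on the further assumption that the stated 95% power refers to 16 pairs. The conclusion does not depend on that SD: across 0.6 to 1.0 the written rule is met at least 99% of the time for any of the gains tabulated, and 90.4% of the time for none.

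**What to change.** Before round 1 data are seen, add to Section 9, for Procedure 3:

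- Keep the existing *not significantly smaller* rule.
- Beside it, test H0: Supertowel reduction ≤ soap reduction against H1: Supertowel reduction > soap reduction, with the one-sided Wilcoxon signed-rank test at the plan's 0.1.
- Claim *more efficacious* only if this H0 is rejected; otherwise report superiority as not shown.
- State that, with both rules in use, some directional verdict arises 19.3% of the time under equality, of which 9.6% is a false superiority claim.

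The cost is a few sentences; the volunteers, pairs and test stay the same. The price is the 19.3% above and limited power for gains below 0.6 log, as shown in step 4.

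Alternatively, reword objective 4 to ask whether the Supertowel is as efficacious as soap, so that it matches Section 9. This costs one phrase but gives up the superiority question.

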3. STUDY DESIGN

To test the efficacy of the Supertowel under the different conditions, we will use a crossover controlled study based and adapted on the protocol of the European Committee for Standardization (EN 1499) which is designed to evaluate the ability of hand-wash agents to eliminate transient pathogens from volunteers’ hands without regard to resident microorganisms. This procedure is based on the “post-contamination treatment” of hands and involves the placement of the test organism (E. coli [ATCC 11229]) on the hands of test subjects, followed by exposure of the test product.

The study will be organized in two rounds of tests. 32 healthy volunteers will be selected for the study. 16 volunteers will be invited for the first round and 16 more for the second round. Each volunteer will receive treatment with all the different procedures the same day of visit to the laboratory.

This is a single centre study conducted in KET’s Scientific Research Centre, Mumbai (India). The recruitment and performance of tests will be done at KET’s Scientific Research Centre, Mumbai (India) Laboratory of India.

3.1 STUDY OUTCOME MEASURES

Reduction of bacteria in pre-contaminated hands of volunteers after using the different test conditions.

3.2 RISKS AND BENEFITS

There are no foreseeable discomforts, distresses, or hazards to which research participants will be exposed. The fabric has been tested previously and the data in the Material Safety Data Sheet (MSDS)(Appendix 2) confirms that material is safe and in previous tests there were no adverse reactions.

The test will be done with non-pathogenic E.coli. After the study is finished, the participants will be asked to wash their hands with medicated soap.

The volunteers will be compensated with a small amount of money (to cover transport cost to the laboratory and subsistence expenses) to participate in the study. There is no other compensation for taking part in this study, but they will be informed that they are contributing to research that could help many others in the future.

4. SELECTION AND WITHDRAWAL OF PARTICIPANTS

4.1 PRE-RANDOMISATION OR PRE-REGISTRATION EVALUATIONS

No diagnostic test needs to be carried out to select the male participants.

4.2 INCLUSION CRITERIA

Volunteers will be recruited by using poster advertisements (Appendix 3) which will be placed within the institution which the laboratory is a part of.

To be eligible volunteers must:

- Be male and older than 18 years old.
- Be physically examined to ensure they are healthy and with healthy skin (without skin disorders like eczema, paronychia, scabies, abrasions, lacerations or skin allergy).
- Have short fingernails with no artificial nails.
- Have no history of drug allergy.
- Not have taken any systemic antibiotic in the two weeks prior to the study, which could otherwise impair the efficacy of the product being tested.
- Remove all forms of jewellery from their hands prior to hand washing, since it has the potential of retain some bacteria, which could affect the recovery pre and post values of the test.

4.3 EXCLUSION CRITERIA

Unhealthy volunteers and volunteers with unhealthy skin, history of drug allergy, taken systemic antibiotics in the previous two weeks of the study will be excluded from the study.

4.4 WITHDRAWAL CRITERIA

Volunteers will be read an information sheet (Appendix 4) where the full study will be explained and where all the procedures for withdrawing from the study will be described. After agreeing to participate in the study, participants will be asked to sign a consent form (Appendix 5).

Participants can withdraw at any time without giving a reason and without having any repercussion. If this is the case, a new volunteer will be recruited and all the data from the withdrawn volunteer will be destroyed.

In the case that a volunteer feels sick or suffers any injury or has a reaction to the product, the participant will be asked to withdraw from the study and appropriate support will be given in the laboratory by [name]. First aid and management of minor health issues will be provided at the laboratory but any more serious health issues will be referred to a nearby health centre. A new volunteer will be recruited and data from withdrawn participant will be destroyed.

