7.2 REPORTING PROCEDURES

Depending on the nature of the event the reporting procedures below should be followed. Any questions concerning adverse event reporting should be directed to the Chief Investigator in the first instance.

The Supertowel has been tested previously and is been considered safe (Appendix 2). There have been no prior adverse events. Therefore, based on this experience no safety issues are anticipated. We don't anticipate that the bar of soap or the sterile oil and soil (used in procedure 4) will produce any adverse effect among participants, as these products are safe and non-pathogenic. For the purpose of this study we use the following definitions for safety reporting:

Definitions used:

Adverse Event (AE): any untoward medical occurrence in a clinical study subject. This includes any incidental findings that may be discovered as a result of the study.

Serious Adverse Event(SAE): any untoward and unexpected medical occurrence or effect that:

- Results in death

- Is life-threatening – *refers to an event in which the subject was at risk of death at the time of the event; it does not refer to an event which hypothetically might have caused death if it were more severe*
- Requires hospitalisation, or prolongation of existing in patients' hospitalisation
- Results in persistent or significant disability or incapacity
- Is a congenital anomaly or birth defect

Medical judgement should be exercised in deciding whether an AE is serious. Important AEs that are not immediately life-threatening or do not result in death or hospitalisation but may jeopardise the subject or may require intervention to prevent one of the other outcomes listed in the definition above, should also be considered serious.

Recording and reporting of procedures:

All adverse events will be recorded and appropriate treatment or referral be provided. For any serious events, the appropriate SAE form should be completed and submitted to the Chief Investigator within 24 hours.

All SAEs will be reported within 24 hours to the Head, Microbiology department from KET's Research Centre/ LSHTM Ethics Committees where in the opinion of the Principal Investigator; the event was thought to be 'related', i.e. resulted from the administration of any of the research procedures.

Contact details for reporting SAEs
Fax:[name] attention to [name]
Please send SAE forms to: [name]
Tel: + (Mon to Fri 09.00 – 17.00)

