8.1 LOSS TO FOLLOW-UP

As the experiments will be done with each volunteer at the same day, loss to follow up is not considered in this study. If for whatever reason a volunteer does not complete all the tests, a new volunteer will be recruited and data from the volunteer not completing all tests will not be considered and will be destroyed.

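### Sections 4.4 and 8.1 destroy the data of withdrawn and non-completing volunteers without exempting adverse-event records, so a non-serious reaction that ends participation could vanish from the trial file

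*Combined protocol and SAP*

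**What the plan says.** Three rules in the combined protocol and SAP order destruction.

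- Section 4.4, voluntary withdrawal: a replacement is recruited and "all the data from the withdrawn volunteer will be destroyed".
- Section 4.4, withdrawal on health grounds: if a volunteer falls ill, is hurt or "has a reaction to the product, the participant will be asked to withdraw from the study". The rule then continues: "A new volunteer will be recruited and data from withdrawn participant will be destroyed".
- Section 8.1, non-completion for any reason: a replacement is recruited and "data from the volunteer not completing all tests will not be considered and will be destroyed".

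Three other provisions concern recording and keeping.

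- Section 7.2: "All adverse events will be recorded and appropriate treatment or referral be provided". An adverse event is defined there as any untoward medical occurrence, so a minor skin reaction counts. For serious events a form is to be completed and "submitted to the Chief Investigator within 24 hours".
- Section 9: data and appropriate documentation are kept for at least 5 years after the study ends.
- Section 10.2: the trial manager holds the consent forms and data collection forms and keeps the research records of recruited participants in safe custody. Hard copies are kept for up to 10 years.

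Section 8 plans no further follow-up, although participants receive the trial manager's contact details. On the product's safety history, section 7.2 states: "There have been no prior adverse events".

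**The concern.** Under section 4.4 a reaction to the product leads to a request to withdraw, and withdrawal leads to destruction of data and replacement. The event that matters for safety is therefore what triggers the loss of the record. If the rule is followed as written and the adverse-event record counts as data, a non-serious reaction that ends participation leaves no trace, and the cohort is refilled to 32. The trial could then be reported as showing no reactions when there was one. That would add to a safety record which sections 3.2 and 7.2 already describe as free of adverse reactions, partly because the contrary evidence had been deleted.

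The plan also does not require the number of replaced volunteers to be kept or reported. It may be recoverable from consent forms and study IDs, but nothing says so.

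**Working it through.** The plan states no figure on this point, so there is none to reproduce. The check sets the rules side by side and then illustrates the size.

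**Which records are at risk**

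1. *Serious event.* Section 7.2 sends a form to the Chief Investigator within 24 hours, so a record exists outside the volunteer's file. Not the gap.
2. *Reaction in a volunteer who completes all tests.* Neither destruction rule applies. Not the gap.
3. *Non-serious reaction before completion, leading to withdrawal.* Section 7.2 requires it to be recorded, but gives no separate route and no retention period. Section 4.4 orders the volunteer's data destroyed, and 8.1 does so again because the tests are incomplete. This is the gap.

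**How the rules fit for case 3**

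- Against 7.2: an event can be recorded and the record later destroyed without breaching the wording, but the purpose of recording is lost.
- Against section 9: destruction at withdrawal does not meet a 5-year minimum, and no exception is written.
- Against 10.2: custody of the research records of recruited participants does not fit with destroying some of them. The 10-year figure is a ceiling and does not itself forbid earlier destruction.

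**Illustration of size**

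Inputs: 32 volunteers, 16 per round (sections 3 and 6.3), held constant by replacement (4.4, 8.1). The number of replaced reactors, k, is an assumption because the documents give no reaction or dropout rate. It is further assumed that no completer reacts.

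Actual proportion = k/(32 + k); retained file = 0/32. Limits are exact two-sided 95% (Clopper-Pearson). With zero events the upper limit is 1 − 0.025^(1/n):

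- n = 32: 1 − 0.025^(1/32) = 10.9%
- n = 16: 1 − 0.025^(1/16) = 20.6%

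| Assumed reactors replaced | Actual (95% CI) | Retained file (upper limit) |
|---|---|---|
| 1, whole trial | 1/33 = 3.0% (0.08 to 15.8%) | 0/32 (10.9%) |
| 2, whole trial | 2/34 = 5.9% (0.72 to 19.7%) | 0/32 (10.9%) |
| 3, whole trial | 3/35 = 8.6% (1.8 to 23.1%) | 0/32 (10.9%) |
| 1, within one round | 1/17 = 5.9% (0.15 to 28.7%) | 0/16 (20.6%) |

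In every row the actual proportion lies below the upper limit of the retained file. Four replaced reactors (4/36 = 11.1%) would be needed to exceed 10.9%. What is lost is the event itself rather than a large shift in the estimate.

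**Efficacy**

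Replacement keeps 16 completers per round, so the number of pairs in the matched-pair comparison, and hence its power, does not change.

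**The case against.** The best reply is that *data* here means bacterial counts. Section 8.1 couples destruction with not considering the data, which is the language of analysis. The phrase covering all data belongs to voluntary withdrawal, while the sentence on reactions says only data. Section 7.2 is the specific rule for adverse events and could be read as governing over a general one. The information sheet, "where all the procedures for withdrawing from the study will be described", may settle the matter, and it was not available. This reading is possible and should be conceded as such. But the protocol nowhere states it, and the destruction rule in 4.4 is attached directly to product reactions.

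A second reply is that the general 5-year rule can coexist with a specific exception for withdrawn volunteers, and that the custody sentence in 10.2 is mainly about secure storage. This weakens the conflict to an inconsistency that needs reconciling; it does not remove it.

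Third, no adverse-event rate is a planned outcome. Section 3.1 lists only bacterial reduction and section 9 plans no safety analysis, so 0/32 is not a figure the plan commits to report. That is correct, and it is why the table is only an illustration.

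A reader might also infer more than the text supports:

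- *That the plan directly contradicts 7.2.* It does not, because 7.2 sets no retention period.
- *That serious events would be lost.* The 24-hour form gives them a separate route.
- *That the same-day record is the only possible source.* Section 8 gives participants a contact, and section 11.2 plans video recording with permission. Neither is planned safety follow-up, but both are channels.
- *That destroying withdrawn volunteers' outcome data is itself a flaw.* It is a defensible choice in the participant's favour.

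**Conclusion.** The point holds in a limited form, and the text should be changed. As written, sections 4.4 and 8.1 allow the record of a non-serious reaction that ends participation to be destroyed. This undercuts the purpose of 7.2 and is inconsistent with sections 9 and 10.2.

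It takes effect only if four things occur together: the reaction is non-serious, it comes before the volunteer finishes, it leads to withdrawal, and the adverse-event record is destroyed along with the counts. In that case one reaction in 33 volunteers would appear as none in 32. The effect on an estimated rate is small; the harm is that a safety event goes unreported. The efficacy comparison and its power are essentially unaffected. Confidence is moderate, because the information sheet could define the term or already promise destruction.

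**What to change.** Reconcile sections 4.4, 7.2, 8.1, 9 and 10.2 by stating in 4.4 and 8.1 that:

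- destruction applies to outcome (bacterial count) data only;
- adverse-event records, the number enrolled, and the number of withdrawn or replaced volunteers with any reason given are always retained and reported.

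Add a matching line to the information sheet. No change is proposed to when a volunteer stops, to replacement, or to the destruction of withdrawn volunteers' outcome data.

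The cost is one or two sentences in the protocol and one in the information sheet. The small downside is that the consent text may need re-approval. Sample size, sequences and the analysis set stay as they are.
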